During part II for control couples, (90 minutes), the case manager will (a) provide a detailed description of the procedure for control group (this will be supported by presenting couples with The Control Group Flowchart for Participants to enhance understanding – see this document in Attachments); (b) oversee and assist couples complete pre-test surveys including the Pre-Program Survey (nFORM) and Pre-test Assessment (Qualtrics) (both surveys combined will take about 90 minutes – For content of assessments please see documents Pre-Program Survey nForm and Pre-Test Assessment in Attachments; (c) provide the couple their compensation in gift cards \$40 per couple (\$20/partner) for assessments; (d) ask partners to sign the Gift Card Receipt (see document in Attachments) after receiving the gift cards; and (e) schedule the couple for their post-test assessment meeting (in 8 weeks) and financial workshop/follow-up assessment (six months from the date of the post-test assessment meeting months). In the event that control couples cannot stay for this second part of the Intake and Enrollment meeting, they will be offered the possibility of completing the pre-program survey nForm and pre-test assessment in paper format or online. If the couple chooses to complete the survey and assessment in paper, they will be provided the questionnaires, the instructions to complete the questionnaire, and a self-addressed envelope to mail the questionnaires. The instructions will explain that they will be mailed the gift cards once the questionnaires are received and that they will be required to fill out a Gift Card Receipt (see document in Attachments). If the option is available and couples agree to it, they may receive the gift cards electronically once we have received the mailed questionnaires. If the couple chooses to complete the survey and pre-assessment online, we will be emailing to each partner the link and the individual passcode and we will be mailing the gift cards or provide them electronically, if this option is available and the couple agrees to it, once they complete the questionnaires.

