The TOGETHER workshop will be offered at FSI, UMD, VT, or designated agencies, schools, or churches. There will be eight offerings in each facility per year. The workshop will be offered in eight sessions (2 hours and 30 minutes each) scheduled on the same day of the week and at the same time. Efforts will be made to offer the sessions in the evenings and on weekends to facilitate participation. Participants complete a 2 minute-session evaluation and a 2-minute homework evaluation within the time allotted to the session. In the last session they complete a 5 minute session evaluation+overall workshop evaluation within the session (see Session Evaluation questionnaire, homework evaluation questionnaire, and session evaluation and overall workshop evaluation questionnaire).

At the first TOGETHER session, couples will complete the Pre Program Survey (nFORM) and the Pre-test Assessment (Qualtrics) before the session begins. Completion of the Pre Program Survey and Pre-test Assessment will take about 90 minutes. For participants both surveys will be collectively referred to as "Pre-Test Survey". Partners will be instructed to complete these surveys in tablets provided by the group facilitators. Couples will receive compensations for

completing assessments in gift cards \$40 per couple (\$20/partner) and each partner will be required to sign and date the Gift Card Receipt Form upon receipt of the gift cards. TOGETHER session facilitators will oversee the completion of the Pre-Test Survey. Participants that fail to attend the first session of the TOGETHER workshop will be mailed the Pre-Test Survey for their completion (see in attachments these two documents: Instructions for Completion of Mailed Pre-Test Survey for Intervention Couples and the Pre-Test Survey (that shows the paper and pencil format for these two surveys combined: Pre-test Assessment and Pre-Program Survey). Participants will be instructed to return the completed surveys on the second session to receive their gift cards. Couples that wish to complete the pre-test survey online instead will be instructed on how to do so.

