The multilevel approach utilizes all data from each time point, retaining as much data as possible when attrition occurs. Analyses controlled for demographic variables that have been associated with relationships (for a review, see Karney & Bradbury, 2020) and financial outcomes (Xiao et al., 2015): Race (White = 1 vs. not), marital status (married = 1 vs. not), gender, age, highest level of education, income, length of relationship in years, number of children, and baseline measurement of the outcome variables. We controlled for baseline differences in the outcome measures in the piecewise multilevel growth model by constraining baseline treatment and group to equality (i.e., constrained longitudinal data analysis; Liang & Sieger, 2000). To facilitate the interpretation of results, we computed Cohen's d effect sizes (group mean difference divided by the pooled within-group standard error) and confidence intervals (CI) for all effects. The Benjamini-Hochberg method (1995) was used for adjusting p values for multiple comparisons as recommended by What Works Clearinghouse for controlling the false discovery rate for studies that have multiple outcome variables.

We used multilevel generalized mixed models for attrition analyses where the outcome variable was a binary indicator of missing. Covariates were demographic variables and baseline measures of outcome measures. As in the main analyses, random effects were included to account for the nesting of individuals within couples. Attrition analyses examined if there were significant differences in demographic and outcome variables between all participants that stayed in the study in comparison with those that dropped out. Differential attrition analysis examined if there were significant differences in demographic and outcome variables between the control group's attrition and the intervention group's. Nonetheless, we accounted by any attrition differences by

including demographic variables as covariates and controlling for baseline measures of the outcomes in all of the analyses.

Relatedly, we assessed baseline equivalence across groups for demographics and outcome variables not only in the entire sample (at initial randomization) but also in the analytic sample (retained at follow-up) to evaluate attrition effects. We controlled for baseline differences in demographic and outcome variables in all analyses.

References

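### The intervention arm's outcome pre-test, and payment for its mailed version, depend on workshop attendance while the control arm's do not, so outcome baselines may be selectively missing and the SAP does not report or handle this

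*Protocol*

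**What the plan says.** Randomisation takes place in Part I of the Intake and Enrollment meeting (Protocol). Both arms also complete the applicant-characteristics and demographic surveys there. The outcome pre-test comes afterwards, by a different route in each arm.

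- **Control** (Protocol, Intake and Enrollment, Part II). The pre-test is done at the meeting with the case manager and paid on the spot. Couples who cannot stay may take paper forms with a return envelope: "The instructions will explain that they will be mailed the gift cards once the questionnaires are received". They may instead use an emailed link, with cards mailed or sent electronically.
- **Intervention** (Protocol, Intervention Couples: TOGETHER Workshop). Part II of intake lists a needs assessment and scheduling but no pre-test. "At the first TOGETHER session, couples will complete the Pre Program Survey (nFORM) and the Pre-test Assessment (Qualtrics) before the session begins". For those absent: "Participants that fail to attend the first session of the TOGETHER workshop will be mailed the Pre-Test Survey for their completion". Then: "Participants will be instructed to return the completed surveys on the second session to receive their gift cards". The section goes on: "Couples that wish to complete the pre-test survey online instead will be instructed on how to do so". It does not say how cards reach those who complete online.
- **Payment rule** (compensation text at the end of the Protocol). Both arms get the same amount for the pre-test, $40 per couple, and assessments are paid if completed. Attendance is a condition only for the workshop incentive and the development-plan meeting.
- **SAP, Data Analysis Plan.** Baseline equivalence of demographics and outcomes is assessed "not only in the entire sample (at initial randomization) but also in the analytic sample (retained at follow-up"). For the attrition models: "Covariates were demographic variables and baseline measures of outcome measures". The main model lists the baseline outcome as a covariate and also constrains baseline means to be equal across arms. The SAP gives no rule for a missing pre-test.

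**The concern.** In one arm only, and after couples know their allocation, the baseline measurement is linked to turning up for the treatment. An intervention couple that never starts has a weaker route to a baseline, and a weaker incentive to supply one, than a control couple that goes home without completing the form. If such couples differ from the rest, for instance in motivation or relationship distress, the intervention couples with a pre-test are a more selected group than the controls with one.

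Two reported results are at stake. An equivalence statement about outcomes at randomisation could be made for what is really the subset with a pre-test. An attrition model that needs baseline outcomes could also omit couples lost before the pre-test, and so understate early loss in one arm.

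**Working it through.** The documents give no pre-test completion rate, so there is no plan figure to reproduce. The check compares the text, then illustrates the size.

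**1. Remote surveys side by side (Protocol)**

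| Survey point | If not done in person | Payment for the remote version |
|---|---|---|
| Control pre-test | Envelope or online | Mailed or electronic, on completion |
| Control post-test | Mailed or online | Mailed or electronic, on receipt |
| Control follow-up | Mailed or online | Mailed or electronic, on receipt |
| Intervention pre-test | Mailed or online | Paper: on return at session 2. Online: not stated |
| Intervention post-test | Mailed or online | Left to the instruction sheet; no session named |
| Intervention follow-up | Mailed or online | Mailed or electronic, on receipt |

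Only the intervention pre-test ties payment for a remote survey to attending a later session. That also conflicts with the closing compensation rule, which asks only for completion.

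**2. Which SAP steps need the pre-test**

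- Equivalence check, demographic half: data come from Part I of intake in both arms. Not affected.
- Equivalence check, outcome half: it can be computed only for couples with a pre-test, whatever the sample is called.
- Attrition models: affected if baseline outcomes are required covariates and rows with missing values are dropped. The SAP does not say.
- Main model: with baseline as part of the longitudinal response, a couple with no pre-test but with later data still contributes. If baseline is also a covariate, that couple is lost unless baseline is imputed. The SAP lists both devices.

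**3. Size**

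From the Protocol: 360 couples per arm. Assumed: proportion with no pre-test p_I = 10–25% (intervention) and p_C = 2–5% (control); gap g = 0.3 SD between couples with and without a pre-test, the same in both arms.

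- Couples without a pre-test: 360 × 0.10 = 36 to 360 × 0.25 = 90 (intervention); 360 × 0.02 ≈ 7 to 360 × 0.05 = 18 (control).
- Differential loss, p_I − p_C, over all pairings: 10 − 5 = 5 to 25 − 2 = 23 percentage points.
- Within an arm, the mean among those with a pre-test differs from the mean of all randomised by p × g. Apparent imbalance is therefore (p_I − p_C) × g: 0.05 × 0.3 = 0.015 SD to 0.23 × 0.3 = 0.069 SD.
- With g from 0.2 to 0.5: 0.05 × 0.2 = 0.010 SD to 0.23 × 0.5 = 0.115 SD.
- If half of these intervention couples complete online, p_I falls to 5–12.5%. The differential is then 5 − 5 = 0 to 12.5 − 2 = 10.5 points, or 0 to 0.105 × 0.3 ≈ 0.03 SD.

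For scale, the chance standard error of a baseline difference is √(2/720) = 0.053 SD if partners are independent (720 people per arm) and √(2/360) = 0.075 SD if they are fully correlated. The range 0.015–0.069 SD is therefore about 0.2 (0.015/0.075) to 1.3 (0.069/0.053) standard errors.

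**The case against.** The strongest reply is that nothing here shows any baseline to be missing. Couples who miss session 1 are sent the survey, and online completion needs no attendance. The compensation text makes any completed assessment payable, so a non-starter who answers online is owed the cards and only their delivery is unstated. The instruction sheet for the mailed intervention pre-test is an attachment outside the documents reviewed and may give another return route. The assumed bias is about one chance standard error or less at most settings. Enrolment was planned to end on 30 September 2020, and the SAP revised on 18 November 2021 is in the past tense, so a change to collection may come too late.

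Much of this stands, and it rules out several stronger readings that a reader might infer:

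- *Intervention non-starters have no baselines, or cannot be paid for one.* The mailed and online routes and the pay-on-completion rule leave this as a risk, not a fact.
- *The problem is confined to one arm.* Controls who leave intake and never return the form also lack a pre-test. The issue is possibly unequal missingness.
- *The SAP checks cannot see these couples at all.* Part I demographics cover them.
- *They are dropped from the attrition or main models.* The SAP does not say the analyses are complete-case, and it describes a model that uses all data from each time point.

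What the reply does not remove is that the session-2 condition is written down, applies in one arm only, and differs from the Protocol's own payment rule. Nor can the outcome half of the equivalence check cover couples who have no outcome data.

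**Conclusion.** The asymmetry is real and worth correcting, but its effect is a possibility of unknown size. Outcome baselines may be missing more often among intervention couples who do not start the workshop. This limits the outcome half of the equivalence check at randomisation and any attrition model that requires baseline outcomes; the demographic half is intact.

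Under the assumed rates and a 0.3 SD gap, the differential loss is 5–23 percentage points and the apparent baseline imbalance about 0.015–0.07 SD. Both are smaller to the extent that couples complete at session 1 or online. An imbalance of that size is modest. The more important consequence is that early differential loss could go unreported while outcome equivalence is described as holding for everyone randomised.

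**What to change.** **Protocol, Intervention Couples: TOGETHER Workshop.** Replace the session-2 condition with the rule already used for controls: a return envelope or link, and gift cards mailed or sent electronically on receipt, whether or not the couple attends. State the same for online completion. This brings the section into line with the compensation text.

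**SAP.**
1. Report pre-test completion by arm, with all randomised couples as the denominator.
2. Add a model of having no pre-test, by arm, using the Part I demographics.
3. Label the outcome-variable equivalence check as covering couples with a pre-test, and give counts by arm.
4. State how missing baselines are handled. Keep couples with later data but no pre-test in the main analysis by treating baseline as part of the response in the constrained model, and not also as a covariate.

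If enrolment has ended, the SAP items are the usable part; they need only data that the plan already collects. The cost is slightly more analysis, some postage or electronic cards, and possibly a higher reported attrition rate in the intervention arm.

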#### Intervention Couples: Progress Meetings and Exit Meeting

Five weeks after the ICDP meeting, intervention couples will meet with the case manager for their first of five progress meetings (approximately five weeks between each progress meeting). The progress meetings occur at VT, UMD, FSI, or designated agencies. At each meeting, the case manager will (a) check progress towards goals established in the ICDP, (b) update the ICDP if necessary, (c) address barriers towards meeting ICDP goals, (d) check safety (e.g., presence of domestic violence), and (e) address any program issues (e.g., attendance to employment trainings, Two of these meetings will be in person and three over the phone and each of them will last around 30 minutes and will require the presence of both partners. However, the two in-person meetings will be conducted over the phone as well if the couple is unable to attend the meetings in person.

At the third progress meeting, case managers will provide the attendance incentives for the TOGETHER workshop. Case manager will provide couples with the gift cards \$80 per couple (\$40/partner) for perfect attendance (8 sessions), \$60 per couple (\$30/partner) for attending seven sessions, and \$30 per couple (\$15/partner) for attending six sessions. After providing the gift cards the case manager will ask both partners to sign and date the corresponding Gift Card Receipt form. If the couple does not attend the meeting in person. The gift cards will be mailed or provided electronically if this possibility is available and the couple agrees to it.

Couples will have a final meeting with the case manager at VT, UMD, FSI, or designated locations 6 months after the last TOGETHER session, which will be approximately five weeks after the fifth case management progress meeting. At this exit meeting, the case manager (a) will make with the couple a final progress assessment toward the goals established by the ICDP, (b) will discuss with the couple their plan for continue working towards the ICDP goals, (c) will invite the couple to complete the follow-up survey in the tablets, (d) will provide \$80 in gift cards (\$40/partner) for completion of the follow-up survey, (e) will ask both partners to sign and date the Gift Card Receipt form, (f) will provide information about the TOGETHER program's Facebook group, and (g) will present the couple with a termination letter (see Termination Letter document in Attachments). If one or both partners cannot attend the meeting in person, the six-month follow-up survey will be mailed to them with instructions on how to complete them and return them to

the program in a self-addressed envelope included in the package (see Instructions for Mailed Follow-up Survey in Attachments). Upon receipt of questionnaires by program staff, the gift cards and Gift Card Receipt Form will be mailed to the couple with instructions to complete the form and mail it back to the program staff in the two self-addressed envelopes provided (see Letter and Instructions for Completion of Gift Card Receipt Form in Attachments). The couple will also be offered the possibility of completing this survey online for which instructions will be provided. If the couple chooses to complete this survey online, gift cards will be mailed or provided electronically if this option is available and the couple agrees to it.

Notes from all case management progress meetings and exit meeting with participants will be entered in the nFORM system. Data entered in these notes will not be used for data analysis by the investigators.

#### Intervention Couples: Employment Services

At the ICDP meeting, case managers at VT, UMD, FSI, or designated agencies and will make referrals to Employment agencies for participants who need job and career enhancement services if needed after they review participants' work status, assess initial needs and job and education goals. Employment services will be provided by the SkillSource Group Inc, in Virginia and WIOA employment centers in Maryland. These agencies are the ones in Northern Virginia and Maryland that manage the federally funded WIOA that provides employment/career support services. The TOGETHER Project budget will be used to hire one employment case manager in each state (VA and MD) (two for the Project) and pay for the job assessment and trainings when participants are not qualified for the federal WIOA program (Workforce Innovation and Opportunity Act provides such services for eligible individuals for free) or other state and locally funded employment services. Case managers will contact employment case managers about the first appointment and communicate about the referral (clients) prior to the first meeting and as long as the Release to Exchange Information with the Employment Agency has been signed by both partners in the couple. Participants will be informed by the case manager and will receive reminders of the first appointment at SkillSource, Inc. and Maryland employment centers. In order to receive employment services and training, participants referred by the present study will have to become participants of those agencies. The release to exchange information signed by participants details the information that we will be exchanged between the two agencies (see earlier description). This exchange will allow for the integration of services as the employment case managers will review the couple's Needs Assessment and ICDP from case managers at the FSI and TWC and our program will have access to whether the participant is eligible for WIOA funded services (otherwise this study pays for services for non-eligible participants), the Individual Employment Plan, and the Employment Services and Trainings received. Qualified trainers will provide job development services, job related education and trainings in these agencies. However, neither the trainers nor the services are the responsibility of this study. We are only responsible for making the referral, collaborating in the exchange of necessary information for the coordination of services, and tracking the number and type of services recommended and received by participants. This integration and tracking of services will last for 6 months from the day of Post-Test Survey. After that day, participation in our study is concluded. However, participants can continue with the services with the employment agencies until their employment goals are met even though their participation in the TOGETHER program has concluded.

Employment case managers will not have access to the nFORM system or any of the surveys completed by participants.

#### Intervention Couples: Booster Session

Intervention couples will be invited to a 3- hour booster session three months after completing the last session of TOGETHER workshop. These booster session will include up to 16 couples and will be co-led by a UMD or VT marriage and family therapy intern and a UMD or VT extension specialist. The booster sessions will occur at VT, UMD, FSI, or designated agencies and will offer an abbreviated version of the contents covered in the 20-hour TOGETHER workshop.

Communication of Case Managers with Group Facilitators and Employment Case Managers

Communication among case managers and employment case managers will only take place if there is a release to exchange information signed by each member of the couple. Providers will communicate primarily through conference calls or in-person meetings. There will be weekly conference calls, or, if possible, in-person meetings (1) between case managers and group facilitators, and (2) between case managers and employment case managers. During these meetings, attendees will go over the list of project participants that they share and will update each other about relevant issues that need to be taken into consideration when working with these couples/individuals. Should communication be necessary beyond the scheduled meetings with the case manager, any of the employment case managers or group facilitators can email and/or make a phone call to the case manager if there is an issue related to the participants that cannot wait to be addressed in the following scheduled meeting. Similarly, the case manager will be able to contact the group facilitators and/or employment case managers if needed before the next scheduled meeting. In all of these communications, only participants' ID (nFORM ID) will be used in any records. Case manager communication with group facilitators and employment case managers have to be entered in the nFORM system that tracks all case management operations.

